6.1.1.1 Pasireotide LAR administration

Pasireotide LAR 60 mg will be administered as an i.m. depot injection once every 28 days (+/- 3 days) starting at Day 1 (visit 2).

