Visit Name	Category	Reference to Section 7.2	Screening Baseline	Core study																	End of core study/Early withdraw (EOS)	Safety FU visit **
				1	2	3	4	5	6	7	8	9	10	11	12	13	14	15	16	17		
Study Day			-28 to-1	1	15	21	29	49	57	85	113	141	169	197	225	253	281	309	337			
Week				2	3	4	7	8	12	16	20	24	28	32	36	40	44	48	52			
Contact IVRS for randomization			X																			
Pasireotide LAR injections (q28d)	D			X			X		X	X	X	X	X	X	X	X	X	X	X	X	X	X***
Everolimus administration (daily)	D			Daily***																		
Core study completion	D																				X	
*Only for patients treated with pasireotide LAR ** The safety FU visit should be performed only for patients who prematurely discontinue study treatment or experience disease progression at week 52. The visit should be performed 56 days after the last dose of pasireotide LAR or everolimus, whichever comes last. ***Pasireotide LAR injection and everolimus should be given at V18 only to patients that continue the extension phase																						

[figure not shown]
[figure not shown]

Table 7-2 EXTENSION PHASE - Visit evaluation schedule

Visit No.	Category	Reference to Section 7.2	Extension phase					End of extension phase /Early withdrawn	Safety FU visit**
			1	2	3	4			
Month of extension phase			3	6	9	12	Every 3 mos		
Vital signs	D	7.2.2.2	X	X	X	X	X	X	
Physical examination	S	7.2.2.1	X	X	X	X	X	X	
Weight	D	7.2.2.3	X	X	X	X	X	X	
WHO performance status	D	7.2.2.4	X	X	X	X	X	X	
Tumor evaluation, frequency at investigator's discretion***	D	7.2.1.1	X	X	X	X	X	X	
Gallbladder assessment, frequency as per tumor evaluation at investigator's discretion	D	7.2.2.6.4	X*	X*	X*	X*	X*	X*	
Pulmonary Function Test	D	7.2.2.6.2	As medically indicated						
Bronchoscopy	D	7.2.2.6.3	As medically indicated						
Chest X-ray, or Chest CT scan	D	7.2.2.6.1	As medically indicated						
ECG	D	7.2.2.7.1	X	X	X	X	X	X	
Cardiac imaging (ECHO or MUGA scan)	D	7.2.2.7.2	As medically indicated						
Hematology	D	7.2.2.5.1	X	X	X	X	X	X	
Biochemistry	D	7.2.2.5.3	X	X	X	X	X	X	
Fasting glucose/insulin/HbA1c (everolimus monotherapy)	D	7.2.2.5.4	X	X	X	X	X	X	
Fasting glucose/insulin/HbA1c (combination)	D	7.2.2.5.4	X	X	X	X	X	X	
Fasting glucose/insulin/HbA1c pasireotide LAR monotherapy	D	7.2.2.5.4	X	X	X	X	X	X	
Blood glucose self monitoring (if applicable)		7.2.2.5.4	Continuous						
Liver Function Tests	D	7.2.2.5.5	X	X	X	X	X	X	

[figure not shown]

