3.4.1 Core phase analysis

For the core analysis, the data cutoff will be the 12 month or end of core phase evaluation and the analysis will take place after the last randomized patient has completed the 12 Month evaluation, or discontinued the study treatment due to progression or start of new anti-cancer therapy.

Only data from the 12 month core phase will be used in the core analyses, any data from the extension phase will be excluded. For patients who do not enter extension phase, safety follow up data (if available) will be included in the core analyses.

All events with start date before or on the 12 month evaluation date and with an end date after the 12 month end date will be reported as '*continuing at the end of the core phase*'. The same rule will be applied to events starting before or on the 12 month evaluation date and not having documented end date. This approach applies, in particular, to adverse event and concomitant medication reports. For these events, the 12 month evaluation date will not be imputed and therefore will not appear in the listings.

Imputation of end date will be performed with the 9 or 12 month evaluation date when needed for specific analyses e.g. exposure and dose intensity computation.

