3.9 Assessment windows, baseline and post-baseline definitions, missing data handling

3.9.1 Assessment windows

Patients will be assessed at baseline (day -28 to -1) and will then attend up to 16 visits during the core study with a separate assessment being completed at the end of the core study (EOCS) (12 months), either completion or early withdrawal. Those patients presenting with clinical benefit and not experiencing unacceptable toxicity at the 12 month visit will continue into the extension phase until progression occurs. They will attend visits every 3 months with a separate assessment being completed at the end of the extension phase (EOEP) when progression occurs, patient withdraws or two years after treatment start of the last evaluable patient. All patients who discontinue study treatment must have safety evaluations 56 days after the last dose of pasireotide LAR or everolimus, whichever comes last. This includes those who didn't enter extension phase due to disease progression at week 52. Endpoints (i.e. EOCS and EOEP) will be summarized as per scheduled visits. Any data from unscheduled

visits (Unsch), will be listed. Early withdrawal visits will continue to be displayed at the EOCS visit i.e. it will not be re-mapped to the most appropriate visit.

Visits will be labeled as follows: Baseline, Day 1, Day 15, Day 21, Day 29, Day 49, Day 57, Day 85, Day 113, Day 141, Day 169, Day 197, Day 225, Day 253, Day 281, Day 309, Day 337, EOCS, 3 Mths Extn, 6 Mths Extn, 9 Mths Extn, 12 Mths Extn, 15 Mths Extn, ..., EOEP, Safety FU, Unsch.

The tumor assessments will be time-slotted using the time windows displayed in Table 2.

Table 2 - Time windows for tumor assessments

Time Window	Planned Visit Timing	Time Window Definition
Week 12	Study Day 85 (Week 12)]0; 126] days or]0; 18] weeks
Week 24	Study Day 169 (Week 24)]126; 210] days or]18; 30] weeks
Week 36	Study Day 253 (Week 36)]210; 294] days or]30; 42] weeks
Week 48	Study Day 337 (Week 48)]294; 351] days or]42; 50] weeks
Week 52	Study Day 365 (Week 52)]351; 379] days or]50; 54] weeks
Week 64	Study Day 449 (Week 64)]379; 491] days or]54; 70] weeks
Week k	Study Day x (Week y) x= k*7+1 ; y=k]x-43; x+41] days or]y-6; y+6] weeks

Study Day 1 = start of study treatment date

Similarly to tumor assessments, week-based time windows [REDACTED]. If more non-missing results fall into a specific time window, then the one will be chosen which is closer to the optimal study day of the specific time window.

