5.4.2 Duration of exposure

Everolimus

The following algorithm will be used to calculate the duration of Everolimus exposure:

Duration of exposure (weeks) = (min(date of last administration of Everolimus, date of data cut-off) – (date of first administration of Everolimus + 1)) / 7.

The duration includes the periods of temporary interruption.

Pasireotide LAR

The following algorithm will be used to calculate the duration of Pasireotide LAR exposure:

Duration of exposure (weeks) = (min(date of last administration of Pasireotide LAR +27, date of death, date of data cut-off) – date of first administration of Pasireotide LAR + 1) / 7.

Combination arm

The duration of exposure in the combination arm will be computed for the individual components separately and combined. The exposure for the individual components will be

calculated using the methods above. The duration of exposure to the study treatment for the combined treatment will be calculated as follows:

Duration of exposure (weeks) = (last date of exposure to any study treatment component – date of first administration of study treatment + 1) / 7.

With the last date of exposure to any study treatment component defined as: max (min(date of last administration of Pasireotide LAR +27, date of death, data cut-off date) for Pasireotide LAR, min(date of last Everolimus administration, data cut-off date) for Everolimus).

Summaries of the exposure to each treatment i.e. duration (weeks) of application of study medication will be presented for the safety set.

The total number of patients who received each component will be summarized, with the combination arm being split into three (Pasireotide LAR, Everolimus and Both). Duration of study treatment exposure will be summarized with means of descriptive statistics.

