5.4.3 Relative dose intensity

Relative dose intensity (RDI) will be summarized separately for each study drug and is defined as follows:

$RDI = DI \text{ (dosing unit / unit of time)} / PDI \text{ (dosing unit / unit of time)}$.

Dose intensity (DI) is defined as follows:

$DI \text{ (dosing unit / unit of time)} = \text{Cumulative dose (dosing unit)} / \text{Duration of exposure (unit of time)}$.

For patients who did not take any drug the DI is by definition equal to zero.

For both Pasireotide LAR and Everolimus the unit of time will be weeks.

Planned dose intensity (PDI) is the assigned dose by unit of time planned to be given to patients as per protocol in the same dose unit and unit of time as that of the Dose Intensity.

$PDI = 10 \text{ mg/day} = 70 \text{ mg/week}$ for Everolimus.

$PDI = 60\text{mg per 28 days} = 15 \text{ mg/week}$ for Pasireotide LAR.

In the combination arm, RDI will be summarized separately for each component, but using the duration of the study treatment exposure, not the duration of each of the components.

Cumulative dose is defined as the total dose taken by the patient during the study treatment exposure and will be summarized for each of the study treatment separately.

For Everolimus total dose = sum of all rows on the dosage administration record of (actual dose * (date of end of medication – date of start of medication + 1 (only '+1' if end date not the same as the start date of the next dose))). If the date of end of medication is missing or after the cut-off date then the cut-off date will be used instead. Note that actual dose is the daily dose a patient has taken, if a dose is taken every other day instead then the daily dose will be halved.

For Pasireotide LAR total dose = sum of all doses recorded on the dosage administration record CRF page.

Mean and median relative dose intensity will be displayed along with exposure summaries. Summary of actual dose intensity, categories of relative dose intensity (<70%, 70 - <90%, 90 - <100% and >=100%) and cumulative dose received summary will be displayed in a separate table.

6 Efficacy evaluation

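### Pasireotide relative dose intensity is inflated when the counted exposure ends before the last depot dose's 28 days are over

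*SAP*

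**What the plan says.** SAP 5.4.3 defines RDI as actual over planned dose intensity, with dose intensity equal to cumulative dose divided by duration of exposure. Planned intensity for pasireotide LAR is 60 mg per 28 days, or 15 mg/week. The numerator is given as: "For Pasireotide LAR total dose = sum of all doses recorded on the dosage administration record CRF page". No cut-off or proration applies to it. For everolimus, by contrast, the same section stops the dose sum at the cut-off date.

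In SAP 5.4.2 the pasireotide exposure ends at "min(date of last administration of Pasireotide LAR +27, date of death, date of data cut-off", in brackets. SAP 3.4.1 defines that cut-off: "For the core analysis, the data cutoff will be the 12 month or end of core phase evaluation". The Amendment 5 rationale in the protocol confirms that it was applied patient by patient.

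Protocol 6.1.1.1 and Table 7-1 schedule injections every 28 days from Day 1 to Day 337. SAP Table 2 puts Week 52 on Day 365. A footnote to Table 7-1 adds: "Pasireotide LAR injection and everolimus should be given at V18 only to patients that continue the extension phase". SAP 3.4.1 states: "Only data from the 12 month core phase will be used in the core analyses, any data from the extension phase will be excluded". Neither document says to which phase the Visit 18 injection belongs.

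In the combination arm, SAP 5.4.3 divides each component's dose by the combined study-treatment duration. The pasireotide term of that duration carries the same two caps.

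**The concern.** The 27 days added after the last injection are there so that every dose brings 28 days into the denominator, matching the planned intensity. The caps at death and cut-off can take some of those days away while the whole dose stays in the numerator. The error can only raise RDI.

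At stake are the RDI mean, the median and the four categories (below 70%, 70 to below 90%, 90 to below 100%, 100% or more), which describe how fully the planned dose was delivered. A patient given the planned dose already falls in the top category, so for such patients the error distorts the mean and median. A patient on a reduced dose can be moved up a category or more.

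**Working it through.** **Inputs.** Planned intensity 15 mg/week and uncapped dose sum (SAP 5.4.3). Exposure end rule (SAP 5.4.2). Core cut-off (SAP 3.4.1). Thirteen injections on Days 1, 29, ..., 337 (Protocol 6.1.1.1, Table 7-1). Planned end of core on Day 365 (SAP Table 2). The Day 92 visit and Day 64 death below are assumptions. Protocol 7.1.4 asks only that the visit after stopping treatment be as soon as possible. The generic guideline in Protocol Appendix 14.1.4.2 puts an end-of-treatment visit within 7 days of the last treatment.

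**Formula.** Days = min(last injection + 27, death, cut-off) − first injection + 1. RDI = [dose ÷ (days/7)] ÷ 15.

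**The plan's own figure.** 60 ÷ (28/7) = 15 mg/week, as stated.

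**Planned schedule without a Visit 18 dose.** The last injection is on Day 337, and 337 + 27 = Day 364, before the Day 365 cut-off. Dose is 13 × 60 = 780 mg over 364 days (52 weeks): 780/52 = 15 mg/week, RDI 100.0%. The rule works here.

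**Other cases under the SAP formula.**

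| Case | Dose (mg) | Days counted | mg/week | RDI |
|---|---|---|---|---|
| Three on-plan doses, stops at the Day 85 visit, not re-dosed | 180 | 84 | 15.00 | 100.0% |
| Fourteen on-plan doses, Visit 18 dose on Day 365 counted | 840 | 365 | 16.11 | 107.4% |
| Four on-plan doses, end-of-core visit Day 92 | 240 | 92 | 18.26 | 121.7% |
| Three on-plan doses, death Day 64 | 180 | 64 | 19.69 | 131.3% |
| Doses 60/60/40/40, end-of-core visit Day 92 | 200 | 92 | 15.22 | 101.4% |

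For the last row, giving each dose its full 28 days yields 200/16 = 12.5 mg/week, RDI 83.3%. The patient is reported at 100% or more instead of 70 to below 90%.

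**Check of the correction.** Multiply the last dose by (days from that injection to the end of counted exposure, inclusive, at most 28)/28. From Day 85 to Day 92, and from Day 57 to Day 64, this is 8 days.

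- Four on-plan doses: 180 + 60 × 8/28 = 197.1 mg; ÷ (92/7) = 15.0 mg/week; 100.0%.
- Death on Day 64: 120 + 60 × 8/28 = 137.1 mg; ÷ (64/7) = 15.0 mg/week; 100.0%.
- Doses 60/60/40/40: 160 + 40 × 8/28 = 171.4 mg; ÷ (92/7) = 13.04 mg/week; 87.0%. This differs from 83.3% because fewer days at 40 mg are counted; the category is the same.

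**Combination arm.** Suppose doses on Days 1, 29 and 57, pasireotide then held, and everolimus continued to Day 112. The SAP's combined duration gives 180/16/15 = 75%. Proration leaves this at 75%, because 28 days or more follow the last injection. Ending the denominator at last injection + 27 would give 180/12/15 = 100% and erase the hold.

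**The case against.** Several objections have force.

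- **The planned schedule is handled correctly.** A reader might infer that RDI exceeds 100% for anyone dosed as planned. It does not: 13 injections with end of core on Day 365 give exactly 100.0%.
- **The Visit 18 case rests on an open reading.** Extension data are excluded from the core analysis, and Protocol Table 7-2 counts extension injections from Visit 18, so treating it as the first extension dose is reasonable. But Table 7-1 also lists it in the core schedule. It is undefined, not shown to be counted.
- **Early stopping need not truncate.** Scheduled scans up to Day 337 fall on injection days, 28 days after the previous dose. A patient who stops there without a further dose has a complete interval. Nothing shows how often the visit comes sooner. SAP 3.4.1 also brings safety follow-up data into the core analysis for patients not entering the extension, so a strict cut at the end-of-core visit is less certain for them.
- **Reductions remain visible.** A reader might infer that dose reductions are hidden. SAP 5.4.1 tabulates reductions and interruptions with reasons, by drug in the combination arm, and cumulative dose is also reported. Only the dose-intensity and RDI summaries can mask them.
- **The contrast with everolimus is not clean.** A reader might infer that only pasireotide looks better delivered than it was. The bracket in the SAP 5.4.2 everolimus formula makes that duration two days short: 364 daily doses over 362 days give 100.6%.
- **RDI is descriptive.** Protocol Section 10 names grade 3-4 and serious adverse events and the frequency of treatment modifications for arm selection, not RDI.

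These limit the scope and the weight of the point. They do not remove the mismatch between an uncapped dose and a capped duration.

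**Conclusion.** The pasireotide RDI rule is wrong as written when death or the patient's core cut-off falls within 27 days of the last counted injection, and it gives a wrong result if the Visit 18 injection enters the core dose. The illustrations run from 107.4% to 131.3% for patients given the planned dose, and one reduced-dose patient moves from the 70 to below 90% category to the top one. These sizes rest on the assumed visit and death days and, for 107.4%, on counting Visit 18.

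The number of affected pasireotide patients cannot be derived. The Amendment 5 rationale reports that 43 of 124 randomized patients completed the core and 41 entered the extension, but these figures cover all arms, including everolimus alone. They neither count truncated intervals nor show that Visit 18 doses were included.

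In the extension analysis, run after the last patient stops treatment, truncation should come mainly from deaths. Efficacy results and the tables of reductions and interruptions are untouched.

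**What to change.** In SAP 5.4.3:

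1. State that the Visit 18 injection is excluded from the core cumulative dose. Treatment given at Visit 18 should then also not set the last-administration date in the core analysis; otherwise an on-plan patient would show 780 mg over 365 days, 99.7%.
2. For dose intensity and RDI only, prorate the last pasireotide dose by (days from that injection to the end of counted exposure, inclusive, maximum 28)/28.
3. In the combination arm, keep the combined study-treatment duration as denominator and apply the same proration, so that a terminal pasireotide hold still lowers RDI.
4. Keep the unprorated cumulative dose in its own summary.

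The cost is a few sentences and a small programming change, with no new data. The core analysis has already been run, so its RDI tables should be checked against this rule and rerun or annotated if programmed as written.

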6.1 Implementation of RECIST

Tumor response and disease progression will be evaluated according to the Novartis guidelines based on RECIST 1.1 criteria (enclosed in protocol Appendix 1), unless otherwise noted.

The evaluation of overall lesion response at each assessment is a composite of the target lesion response, non-target lesion response and presence of new lesions as shown below. This information will be captured on the CRF.

Table 4 - Evaluation of overall lesion response

Target lesions	Non-target lesions	New Lesions	Overall lesion response
CR	CR	No	CR ¹
CR	Non-CR/Non PD	No	PR
CR, PR, SD	UNK	No	UNK
PR	Non-PD and not UNK	No	PR ¹
SD	Non-PD and not UNK	No	SD ^{1,2}
UNK	Non-PD or UNK	No	UNK ¹
PD	Any	Yes or No	PD
Any	PD	Yes or No	PD
Any	Any	Yes	PD

¹ This overall lesion response also applies when there are no non target lesions identified at baseline.
² Once confirmed PR was achieved, all these assessment are considered PR.

A listing of the tumor assessments and responses will be presented for the full analysis set after completion of core phase and extension phase analyses. This will include evaluation number, type of lesion (target, non-target, new), overall assessment, number, location, measurement method, evaluation date, longest diameter (cm), lesion status and an overall lesion response as per the investigator. Patients who discontinue study treatment after 12 months of treatment without evidence of progression or for reasons other than disease progression will continue to have tumor evaluation assessments unless consent is withdrawn. These will be flagged in this listing.

Another listing of lesion locations and descriptions will also be produced for the full analysis set. This will include the evaluation number, the type of lesion (target, non-target, new), the

number, the evaluation date, the location, the description, the measurement method and the measurement method detail.

For each time to event assessment, the assessment date is calculated as follows:

- the latest of all measurement dates for assessment with overall lesion response = CR, PR, SD or UNK.
- the earliest of all measurement dates for assessments with overall lesion response = PD.

6.2 Source for overall lesions response

The tumor endpoints derivation is based on the sequence of overall lesion responses at each assessment/time point. Of note, no central review is planned in this study, however all scans will be locally stored. If the decision is taken at a later point to perform a central review, then the RAP will be amended.

Investigator (local radiology) reported overall lesion response at each assessment will be recorded on the eCRF and will be used for the primary endpoint derivation.

6.3 Primary efficacy evaluation

6.3.1 Variable

The primary efficacy endpoint is defined as the proportion of patients who are progression-free at Month 9 (PFR-9) based on RECIST V. 1.1.

All CT scans and MRI will be assessed and validated at the local sites throughout the trial.

The investigator evaluation of overall lesion response will be used for the assessment of the primary efficacy endpoint.

Patients with CR, PR or SD at Month 9 will be considered as “progression-free”.

Patients with missing tumor assessment, or with overall lesion response “unknown” at Month 9 will be considered as “non progression-free”, unless any of the following assessments at week 48 or week 52 indicate CR, PR or SD, in which case the patient will be considered as progression-free at Month 9.

Patients discontinuing the study for any reason prior to the 9 month assessment will be considered as “non progression-free”.

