10.4.3 Handling of missing values/censoring/discontinuations

The definition of the primary variable is based on RECIST 1.1 criteria.

The evaluation of overall lesion response at each assessment is a composite of the target lesion response, nontarget lesion response and presence of new lesions as shown below in [Table 10-1](#).

Table 10-1 Overall lesion response at each assessment

Target lesions	Non-target lesions	New Lesions	Overall lesion response
CR	CR	No	CR ¹
CR	Non-CR/Non-PD	No	PR
CR, PR, SD	UNK	No	UNK
PR	Non-PD and not UNK	No	PR ¹
SD	Non-PD and not UNK	No	SD ^{1, 2}
UNK	Non-PD or UNK	No	UNK ¹
PD	Any	Yes or No	PD
Any	PD	Yes or No	PD
Any	Any	Yes	PD
CR, PR, SD	UNK	No	UNK

Target lesions	Non-target lesions	New Lesions	Overall lesion response
¹ This overall lesion response also applies when there are no non target lesions identified at baseline. ² Once confirmed PR was achieved, all these assessments are considered PR.			

The evaluation of overall lesion response at Month 9 will be used for the assessment of the primary efficacy endpoint.

Patients discontinuing the study for any reason prior to the 9 month assessment, or with missing tumor assessment, or with overall lesion response “unknown” will be considered as “non progression-free”. Only patients in CR, PR or SD at Month 9 will be considered as “progression-free”. Therefore, the proportion of patients who are progression free at 9 months is equivalent to the disease control rate (DCR).

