10.8 Sample size calculation

A Fleming single stage design will be employed for each arm. Let p_0 be the highest proportion of patients progression-free at Month 9 which would indicate that the treatment is clearly ineffective, and p_1 be the minimum required proportion of patients progression-free. The trial tests the null hypothesis H_0 that the observed proportion of patients progression-free, p , is less than or equal to p_0 against the alternative hypothesis H_1 that p is greater than or equal to p_1 . It consists of entering a predetermined number of subjects and deciding in favor of p_0 or p_1 based on the success rate observed by using an appropriate cut-off between p_0 and p_1 . If the number of responses is greater than or equal to $R+1$, p_0 is rejected. If the number of responses is less than or equal to R , p_1 is rejected.

In this trial, p_0 and p_1 have been set equal to 0.20 and 0.45, respectively. Forty (40) patients are planned to be randomized in each treatment group. If the number of responses is 13 or more, the hypothesis that $p \leq p_0 = 20\%$ is rejected with a target alpha error rate of 5% and an actual alpha error rate of 4.3%; if the number of responses is 12 or less, the hypothesis that $p \geq p_1 = 45\%$ is rejected with an actual beta error rate of 4%.

Table 10-2 Design features for single-arm trials

p0	p1	Target		Cut-Off R + 1	N	Actual	
		alpha	beta			alpha	beta
20%	45%	5%	10%	13	40	4.3%	4%

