14.1.4.1 Study/project specific decisions

For each study (or project) various issues need to be addressed and specified in the protocol or RAP documentation. Any deviations from protocol must be discussed and defined at the latest in the RAP documentation.

The proposed primary analysis and potential sensitivity analyses should be discussed and agreed with the health authorities and documented in the protocol (or at the latest in the RAP documentation before database lock).

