ECHO	Echocardiogram

ECOG	Eastern Cooperative Oncology Group
EOCS	End of core study
EOEP	End of extension phase
EOT	End of treatment
FAS	Full Analysis Set
FEV1	Forced expiratory volume in 1 second
FPFV	First patient, first visit
FVC	Forced vital capacity
GGT	Gamma-glutamyl transpeptidase
H0	null hypothesis
H1	alternative hypothesis
HbA1c	Hemoglobin A1c subtype (glycated hemoglobin)
HDL	High density lipoprotein
IGF	Insulin-like growth factor
IHC	Immunohistochemistry
ILD	Interstitial Lung Disease
i.m.	Intramuscular
INR	International Normalized Ratio
ITT	Intent-to-Treat
K-M	Kaplan-Meier
LAR	Long-Acting Release
LDL	Low density lipoprotein
LLN	Lower limit normal
LPLV	Last patient, last visit
MedDRA	Medical Dictionary for Regulatory Activities
MRI	Magnetic Resonance Imaging
mTOR	mammalian target of rapamycin
MUGA	Multiple-Gated Acquisition
NA	Not Applicable
NCI	National Cancer Institute
NET	Neuroendocrine Tumor
NEU	Neutrophils

p.o.	per os/by mouth/orally
PD	Progressive Disease
PFR-9	Progression-free at Month 9
PFS	Progression-free survival
PFT	Pulmonary function test
PI3K	Phosphoinositide 3-kinase
PP	Per-Protocol
PR	Partial Response
PTT	Partial prothrombin Time
RAP	Reporting Analysis Plan
RDI	Relative dose intensity
RECIST	Response Evaluation Criteria In Solid Tumors
RNA	Ribonucleic acid
SAE	Serious Adverse Event
SD	Stable disease
SGOT	Serum glutamic oxaloacetic transaminase
SGPT	Serum glutamic pyruvic transaminase SSC
TC	Typical carcinoid
T3	Tri-iodothyronine
T4	Levothyroxine
TEAE	Treatment-emergent adverse event
TSH	Thyroid stimulating hormone
TTP	Time to progression
ULN	Upper Limit Normal
Unsch	Unscheduled visit
UNK	Unknown
WBC	White Blood Cell
WHO	World Health Organization

1 Statistical methods planned in the protocol

This Report Analysis Plan (RAP) contains details of the statistical methods that will be applied for the final analyses to be incorporated into the CSR. This document is based on the clinical trial protocol version no. 5 dated November 7, 2016.

The purpose of this study is to assess the efficacy and safety of pasireotide long-acting release (LAR) and everolimus alone or in combination.

The rationale for this study is based on both preclinical and clinical considerations:

- Combined inhibition of the IGF-1-, the PI3K- and the mTOR-pathways by pasireotide and everolimus may control tumor growth more effectively than either compound alone.

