The end of the study is defined as the last visit two years after treatment start of the last randomized patient or when all patients have progressed whichever comes earlier.

Data will be analyzed by [REDACTED] according to the data analysis section 10 of the study protocol which will be available in Appendix 16.1.1 of the Clinical Study Report (CSR).

2 Discrepancies between RAP and protocol-specified analyses

The following discrepancy exists between the Reporting Analysis Plan (RAP) and the study protocol version 05, dated 7th November 2016. This discrepancy has become apparent during development of the RAP.

[REDACTED]

[REDACTED] At the RAP review stage it was decided that 95% confidence intervals will be displayed instead following template conventions and presentation methods for other parameters.

3 Statistical and analytical plans

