6.3.2 Statistical Hypothesis, model and analysis

Single-stage phase II trials are frequently undertaken to determine whether a new procedure or treatment is likely to meet a basic level of efficacy before comparing it with the standard technique in a larger randomized phase III trial. This study is of a single stage design, which is defined as follows. Let p_0 be the highest proportion of patients progression-free at Month 9 which would indicate that the procedure or treatment is clearly ineffective, and p_1 be the minimum required proportion of patients progression-free to show that the procedure or treatment is effective. The trial tests the null hypothesis H_0 that the proportion of patients progression-free, p , is less than or equal to p_0 against the alternative hypothesis H_1 that p is greater than or equal to p_1 . It consists of entering a predetermined number of patients and

deciding in favor of p_0 or p_1 based on the success rate observed by using an appropriate cut-off between p_0 or p_1 . In a single-stage design, if the number of responses is greater than or equal to $R+1$, the hypothesis that p is less than or equal to p_0 is rejected. If the number of responses is less than or equal to R , the hypothesis that p is greater than or equal to p_1 is rejected.

In this trial, p_0 and p_1 have been set equal to 0.20 and 0.45, respectively. Forty (40) patients are planned to be randomized in each treatment group. If the number of responses is 13 or more, the hypothesis that $p \leq p_0 = 20\%$ is rejected with a target alpha error rate of 5% and an actual alpha error rate of 4.3%; if the number of responses is 12 or less, the hypothesis that $p \geq p_1 = 45\%$ is rejected with an actual beta error rate of 4%.

In the case where more than 40 patients are randomized to one arm, the required number of responses to reject the null and alternative hypotheses will be computed using the methodology described in Fleming's paper [Fleming 1982]. R Codes below compute the cutoff (RstarPlus1) to reject the null hypothesis for different sample sizes.

For example, with 41 patients, the required number of responses to reject the null hypothesis is still 13 responses, and with 42 patients the required number is 14 responses.

```
fleming <- function(n){
p.0 <- 0.2
Z <- qnorm(0.95)
N <- n
s <- round(N * p.0 + Z * sqrt((N * p.0 * (1 - p.0)))) + 1
thres <- list(N = N , RstarPlus1 = s)
return(thres)
}

n <- 40:45
f <- sapply(n, fleming)
f

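### The protocol counts a missing or unknown Month 9 scan as failure, the SAP can count it as success, and the reported counts have no margin over the SAP cut-offs

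*SAP*

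**What the plan says.** Protocol 10.4.3 bases the primary endpoint on the overall lesion response at Month 9. A patient who discontinues earlier, has no tumour assessment, or has an unknown response is a failure. The section closes the list without exception: "Only patients in CR, PR or SD at Month 9 will be considered" progression-free.

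SAP 6.3.1 repeats the failure rule for a missing or unknown Month 9 response and then adds "unless any of the following assessments at week 48 or week 52 indicate CR, PR or SD". In that case the patient is counted as progression-free at Month 9. Discontinuation before the Month 9 assessment remains a failure in both documents.

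On timing, SAP 3.9.1 states: "The tumor assessments will be time-slotted using the time windows displayed in Table 2". In that table the week 36 (Month 9) window covers days 211 to 294, week 48 covers days 295 to 351, and week 52 covers days 352 to 379.

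Both texts are current. SAP Section 1 says: "This document is based on the clinical trial protocol version no. 5 dated November 7, 2016". SAP Section 2 opens with "The following discrepancy exists between the Reporting Analysis Plan (RAP) and the study protocol version 05", in the singular. Its readable part concerns confidence intervals; some of the section is redacted.

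On the decision rule, Protocol 10.8 says "Forty (40) patients are planned to be randomized in each treatment group" and sets the cut-off at 13 or more. SAP 6.3.2 extends the cut-off to larger arms: 13 for 41 patients, while "with 42 patients the required number is 14 responses". The Amendment 5 rationale in the protocol reports 13/41 for pasireotide LAR, 13/41 for the combination and 14/42 for everolimus, and concludes that the primary objective was met.

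**The concern.** The same patient fails under one document and succeeds under the other. The exception works in one direction only: it can turn a failure into a success and never the reverse. The 20%/45% hypotheses and the cut-offs are unchanged between the two documents.

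The strict rule looks deliberate. The Amendment 4 rationale, which agrees with the current Protocol 10.4.3 on this point, presents it as a way to avoid bias, and changes the endpoint timing, the sample-size assumptions and the decision rule as a consequence of the same decision.

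Each arm's go/no-go decision is at stake. The documents do not say which definition produced the reported counts or whether any patient entered through the exception. The same counts also feed the Bayesian choice of best arm in SAP 6.3.3, where the SAP's own example gives probabilities of 0.4 and 0.60 for 13 and 14 successes out of 40.

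**Working it through.** **Inputs.** p0 = 0.20, p1 = 0.45, N = 40, cut-off 13 (Protocol 10.8, SAP 6.3.2); the cut-off formula in the SAP 6.3.2 code; tumour windows (SAP 3.9.1, Table 2); reported counts (Protocol, Amendment 5 rationale). The number of patients classified through the exception is not given. Call it k per arm, with k = 0 or more.

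**Reproducing the plan's figures.** For X binomial with N = 40:

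- P(X ≥ 13 | p = 0.20) = 0.0432, stated as 4.3%.
- P(X ≤ 12 | p = 0.45) = 0.0386, stated as 4%.

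SAP cut-off = round(0.2N + 1.645 × √(0.16N)) + 1:

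- N = 40: 12.16 rounds to 12, cut-off 13.
- N = 41: 12.41 rounds to 12, cut-off 13.
- N = 42: 12.66 rounds to 13, cut-off 14.

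All match the documents.

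**Where the later scan lies.** Planned Month 9 is day 253. The exception accepts scans from day 295 to day 379: 295 − 253 = 42 days (6 weeks) and 379 − 253 = 126 days (18 weeks). Some would be late Month 9 scans and others Month 12 scans.

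**Margin over the SAP cut-off.** 13 − 13 = 0 (pasireotide LAR), 13 − 13 = 0 (combination), 14 − 14 = 0 (everolimus).

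**Effect of removing k successes**, if the reported counts were derived under the SAP rule. With k = 0 nothing changes. With k = 1 in an arm:

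| Arm size | Successes | SAP cut-off | Exact P(X ≥ x) at 20% | Exact 95% CI |
|---|---|---|---|---|
| 41 | 13 | 13 | 0.0521 | 18.1% to 48.1% |
| 41 | 12 | 13 | 0.1022 | 16.1% to 45.5% |
| 42 | 14 | 14 | 0.0298 | 19.6% to 49.5% |
| 42 | 13 | 14 | 0.0621 | 17.6% to 47.1% |

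Any k above 1 also misses. For the two 41-patient arms, 12 is below both the SAP cut-off and the protocol's 13. For everolimus, 13/42 misses only the SAP cut-off of 14; the protocol states a cut-off for N = 40 alone.

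**Illustration only.** Suppose the true rate under the protocol rule is 20% and an assumed 2% to 5% of patients are added by the exception. Then P(X ≥ 13 | N = 40) is 8.3% at 22% and 17.9% at 25%, against 4.3% with none added. The added fraction is an assumption, and this is not the type I error of the SAP-defined endpoint.

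**The case against.** The best defence is that the consequence is hypothetical: nothing shows that any patient was classified through the exception. The group it can reach is narrow. Early discontinuation is failure in both documents, and the Month 9 window already runs 12 weeks, from day 211 to day 294. Only a patient still on study, with no evaluable scan in that window and a later CR, PR or SD, qualifies. For such a patient the later response is real evidence of not having progressed at Month 9, so the SAP rule is a defensible way to classify an absent scan.

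Protocol Appendix 1, section 14.1.4.1, also leaves room for it: "Any deviations from protocol must be discussed and defined at the latest in the RAP documentation". The 41- and 42-patient denominators need the SAP's cut-offs, which suggests that the SAP governed the analysis. The redactions in SAP Section 2 and the change history limit what can be said about disclosure, and no readable entry suggests that the exception was added after results were known. The planned listing in SAP 6.1 would identify the patients concerned, and the 9-month Kaplan-Meier estimate in SAP 7.1 does not depend on this rule.

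Most of this stands. It limits the claim to a conditional one and makes the SAP rule a reasonable sensitivity analysis, or a reasonable primary rule if openly adopted. It does not remove the conflict. The Appendix permits a departure, but the readable SAP does not identify this one as a departure. With zero margin in all three arms, a narrow exception is enough to matter.

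**Conclusion.** The concern holds. Two current documents define the primary endpoint differently for a missing or unknown Month 9 scan, and the SAP's version is the more favourable. One success obtained through the exception would put that arm below its SAP cut-off under the protocol rule.

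This rests on three conditions: that the reported counts used the SAP rule, which the documents do not state; that at least one patient in the arm was reclassified, which is unknown and may be false; and, for everolimus, that the SAP cut-off of 14 applies at 42 patients. No arm is shown to have failed. If nobody was reclassified, the conclusion is unchanged, but these documents do not let a reader establish that. Because the reported success in every arm depends on this undisclosed number, it must be resolved.

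**What to change.** - In SAP 6.3.1, apply the Protocol 10.4.3 rule to the Fleming decision and present the week 48/52 rule as a labelled sensitivity analysis.
- For each arm, report the number of patients classified through the exception and the study day of the scan used.
- For each arm, give the success count and exact confidence interval under both rules.
- List the departure in SAP Section 2.
- If the sponsor keeps the SAP rule as primary, amend Protocol 10.4.3 to match and still report the count under the existing protocol rule.

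The cost is a wording change, one line in SAP Section 2 and two extra rows in the primary table. The evaluation dates and investigator responses are already in the SAP 6.1 listing. If nobody was reclassified, one sentence settles the matter; otherwise the success count falls in the arms affected.
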